Step 4.01b Training on eSight Eyewear Controls: The subject will receive complete training on the features and controls of eSight Eyewear. This will include a demonstration of

1. Using the HDMI input for computer use and television viewing, including using the motion sensors in the device to control panning across the scene.
2. Using the various binary colour modes to improve reading capability.
3. Various other features such as saving images, etc.

Tests 4.02 through 4.07 below are repeats of previous tests, but using eSight Eyewear.

Step 4.02 Acuity Test – with eSight Eyewear (ETDRS or Snellen)

Step 4.03 Mars Contrast Sensitivity Test – with eSight Eyewear

Step 4.04 n/a

Steps 4.05 through 4.08 may be administered by a Research Assistant or a similarly suitable staff person at the clinic (e.g.: CLVT, OT, etc.).

Step 4.05 Minnesota Low Vision Reading Test (MN READ) – with eSight Eyewear

Step 4.06 Cohn-Kanade Facial Recognition Test – with eSight Eyewear

Step 4.07 Melbourne Low-Vision ADL Index Test (MLVAI) – with eSight Eyewear

Step 4.08 Introduction to eSkills Program³⁶: The subject will be introduced to eSight's "eSkills Program". This is a program which guides the individual through various activities, helping them to understand how to use the eSight controls to optimize their functional visual performance for various activities. While in clinic, Site staff will guide the Subject through session one of the eSkills program.

STEP 5: Take-Home Trial, Month One

The subject will now take the eSight Eyewear with them for a period of about four weeks, during which they will be encouraged to use eSight Eyewear for as many of their ADLs as possible.

³⁶ "eSkills Proficiency Program", Oct 30, 2014.

The subject will be trained that there are certain ADLs that are not permitted, such as driving or operating any sort of dangerous machinery (e.g.: power tools), and walking or performing other mobility tasks while using the device in “immersive” mode. Other ADLs will be prescribed, using eSight to purchase a coffee, using eSight to attend an event where distance viewing is required (e.g. church, theatre, wedding, conference, classroom, etc.), watching television, using a computer, social event, etc.

Site staff will contact the subject by telephone in accordance with the “eSkills Proficiency Program” as follows:

- **Day 9:** verify Session One steps are satisfactory, confirm commitment to proceed with session Two steps. This interaction can occur within a window of ± 2 days of Step 4.
- **Day 16:** Verify Session Two steps are satisfactory, confirm commitment to proceed with Session Three steps. This interaction can occur within a window of ± 2 days of Step 4.
- **Day 23:** Verify Session Three steps are satisfactory, confirm commitment to proceed with Session Four steps, and confirm one-month check in appointment. This interaction can occur within a window of ± 2 days of Step 4.

STEP 6: Subject Visit – Midterm Assessment

Step 6 must occur within 26-34 days of Step 4.

Step 6.01 The purpose of this visit is to assess the subject’s progress with the eSight device, and provide additional guidance and training as required. Part of this visit will be to assess the Subject’s self reported progress with the goals identified in Step 3.01 above, and to work with the Subject to improve their achievement of these goals through further device training. If necessary, the researcher may contact eSight to learn goal-specific ways that eSight Eyewear can be used. This visit may be conducted in-clinic.

Step 6.02 Also in this visit, the Subject will complete Session Four, the final part of the eSkills program.

STEP 7: Take-Home Trial, Months Two & Three

The subject will again take the eSight Eyewear home with them, this time for a period of two more months.

STEP 8: Telephone Survey

Within 86-94 days of Step 4 (total of three months), subjects will be contacted by the Third Party Surveyor to revisit the VFQ-48, and RAND SF-36 questionnaires³⁷.

³⁷ In the case of Johns Hopkins University Wilmer Eye Institute, research assistants from the institute will conduct Step 2. These research assistants will be dis-associated from the PI and other researchers who have face-to-face interaction with the subject.

Step 8.01 Final VA LV VFQ-48 Questionnaire

Step 8.02 Final eSight-8 Questionnaire

SETP 9: Final Assessment

Within 86-94 days of Step 4, subjects will be required to come to the clinic for a two hour assessment. Subjects will again repeat various supervised tasks and a VA LV VFQ-48 questionnaire to assess improvements in their functional visual performance compared to baseline.

Duration 2-3 hours

Step 9.01 through 9.03 may be administered by a Research Assistant or a similarly suitable staff person at the clinic (e.g.: CLVT, OT, etc.).

Step 9.01 Re-Assessment of Goals Established in Step 3.01: The Research Assistant or Site Administrator will reassess the Subject's satisfaction with their performance of the personal goals as reported in Step 3.01.

Step 9.02 Re-administration of RAND SF-36 Questionnaire

Tests 9.03 through 9.09 below are repeats of previous tests, intended to assess changes in visual function and functional visual performance over time using eSight Eyewear.

Steps 9.03 through 9.05 are administered by the eyecare physician (Optometrist or Ophthalmologist), or suitably trained and supervised clinical staff.

Step 9.03 Acuity Test – with and without eSight Eyewear (ETDRS or Snellen)

Step 9.04 Mars Contrast Sensitivity Test – with eSight Eyewear

Step 9.05 n/a

Steps 9.06 through 9.09 may be administered by a Research Assistant or a similarly suitable staff person at the clinic (e.g.: CLVT, OT, etc.).

Step 9.06 Minnesota Low Vision Reading Test (MN READ) – with eSight Eyewear

Step 9.07 Cohn-Kanade Facial Recognition Test – with eSight Eyewear

Step 9.08 Melbourne Low-Vision ADL Index Test (MLVAI)

Step 9.09 Final comments, opportunity for freeform feedback, relinquishment of the device.

5. Withdrawal from the Study

A subject may withdraw or be removed from the study at any time without prejudice for any of the following reasons:

- The subject wishes to withdraw
- Occurrence of any serious or adverse device-related effect that is considered by the investigator to represent an unacceptable risk to the subject's physical or mental well-being.
- Occurrence of any physical or mental illness that affects the subject's further participation.
- The subject fails to comply with the requirements of the study.

Time permitting, subjects that withdraw from the study will be replaced by other candidates. Every effort will be made to have withdrawn subjects complete the follow-up procedures (Part 4).

6. eSight Support for Clinical Sites

At each site, before the Study commences, eSight staff will visit the Study location to provide one full day of training with the eSight Eyewear device. This will include the following:

- Training on device demonstration and fitting (trial lenses, adjustment of forehead strap and headband, P.D. adjustment, etc.).
- Explanation of device controls (zoom, video modes, OS/OD displays on/off, saving images).
- Training on various ADLs (bioptic and immersive activities).
- Using direct video feed for television and computer use.
- Facial Recognition test training.
- Training on the eSkills program.
- Training on study management, data collection, and CRF administration.

In addition, eSight will visit site locations for clinical visit number two, during which fitting and training of the subject is provided. To control costs, sites will attempt to consolidate multiple subjects in a single day for this step in the process. This means that each study site will have two or three visits by eSight staff over the course of the study, assuming 8-12 subjects per study site.

7. Adverse Events

An adverse event (AE) is defined as any untoward medical occurrence, including deterioration of a pre-existing medical condition in a patient or clinical investigation subject which may or may

not have a causal relationship with the investigational product (i.e. eSight Eyewear). An AE can therefore be any unfavourable and unintended sign, symptom, or disease temporally associated with the use of an investigational product, whether or not considered related to the investigational product.

The Principal Investigator/Sub-Investigator will assess the relationship of all adverse reactions to the investigational product, using the following scale:

Probable	A clinical event, including laboratory test abnormality, with a reasonable time sequence to device usage, unlikely to be attributed to concurrent disease or other drugs or chemicals, and which follows a clinically reasonable response on withdrawal.
Possible	A clinical event, including laboratory test abnormality, with a reasonable time sequence to device usage, but which could also be explained by concurrent disease or other drugs or chemicals. Information on device withdrawal may be lacking or unclear.
Unlikely	A clinical event, including laboratory test abnormality, with a temporal relationship to device usage which makes a causal relationship improbable, and which other drugs, chemicals or underlying disease provide plausible explanation.
Unrelated	This category is applicable to Aes which are judged to be clearly and incontrovertibly due to extraneous causes (diseases, environment, etc.) and do not meet the criteria for device relationship listed for the above mentioned conditions.

The incidence, severity and duration of all adverse events will be recorded according to the following scale:

Mild	Adverse event resulting in discomfort, but not sufficient to cause interference in normal daily activities.
Moderate	Adverse event resulting in discomfort that is sufficient to cause interference in daily activities.
Severe	Adverse event resulting in discomfort causing an inability to carry out normal daily activities.

All severe Aes, whether or not the event is deemed device-related, will be reported to the Sponsor by telephone within twenty-four hours of being aware of a severe AE, followed by a written report within five business days.

Practically speaking, the risk of adverse events with eSight Eyewear is extremely low. The most significant risk is injury resulting from disorientation or poor psycho-spatial hand-eye performance related to using the device to perform any task where injury may be possible. Some examples include: Falling or tripping while wearing the eSight device in an immersive mode while walking; risk of burns while cooking or drinking hot beverages; participating in specifically prohibited activities such as riding a bicycle or driving.

8. Stopping Criteria

Should any AE necessitate that a specific Subject must terminate their participation in the Study, the Site Administrator will, within their best judgement, inform his/her counterparts at the other Study Sites so that they are prepared for similar circumstances at their respective Study Sites.

9. Study Materials

If the study site does not already own any of the materials below, they will be provided by eSight at the beginning of the study:

- **Case Report Form (CRF):** This form is used to record and track the subject's progress through the course of the study. For each unique CRF, Subject identifying information appears on the first page of the form only. Subsequent pages show only a unique identification number provided by the Study Sponsor. CRFs returned to eSight for

analysis will be “de-identified”, referenced by this identification number only. The first page will be removed.

- **ETDRS Acuity Chart**
- **Mars Contrast Chart**
- **MN READ Test Charts**
- **Clinical Unit:** This unit is identical to the subject’s configured unit except that it incorporates provision for trial lenses so that it may be used on multiple subjects.
- **eSight Facial Recognition Test:** Materials required to conduct this test and record results³⁸.
- **MLVAI Materials**
- **Subject’s Unit:** If the subject is deemed a suitable candidate for an extended evaluation period, they will receive a unit with the user interface customized for them, along with their prescription lenses incorporated, if applicable.
- **Materials for In-Clinic ADL Testing:** Telephone book, kitchen ingredients, etc.

10. Analysis

Some of the data gathered through the course of this study is subjective, and will be used by eSight to prioritize ongoing improvements to the device.

The minimum objective data that will be reported is acuity, contrast, reading speed, without eSight Eyewear at the beginning of the trial, and with eSight Eyewear at its conclusion.

Further objective data is the comparison between the initial VFQ, and RAND SF-36 scores, and the change, if any, in score at the conclusion of the study.

Data analysis will be conducted using IBM SPSS Statistics version 22. The data will be pooled from all testing sites by the Study Manager. Before merging of the data, any systematic differences among testing sites will be assessed. Should such differences exist, they will be considered in subsequent analyses.

Repeated measures Analysis of Variance (ANOVA) and t-tests will be used to compare the effect of the eSight devices on all dependent variables that adhere to the assumptions of parametric data analysis (continuous variables, normal distribution etc.). Categorical variables or those who do not adhere to parametric assumptions will be compared using repeated-measures non-parametric techniques (e.g. Friedman Test). Qualitative data will be analyzed using qualitative description (Sandelowski, 2000).

³⁸ Requires 22” monitor with HDMI input. To be provided by eSight in the event that the study location does not have one available.

The eSight device contains an electronic logging capability, wherein daily on-time hours, and user commands (e.g.: zoom in/out, focus distance, increase/decrease contrast, etc.) are saved to an SD card. No images or video or other information that may personally identify the subject is recorded. These electronic logs may be used to validate user reported usage data³⁹.

Methodological Limitations: Given the multi-site nature of the study, it is possible that inter-site differences may occur, based on recruitment possibilities or slight differences in procedural or testing administration differences. The research teams will closely work together with eSight during the preparation phase, in order to minimize such differences. In addition, before data are pooled across sites, statistical comparison will be conducted in order to detection and possibly compensate statistically for such site differences.

As for the limited follow-up time of 3 months, the current study may be limited in its ability to show long-term benefits (or device abandonment). However, follow-up and continuation possibilities are currently being discussed, in order to eventually examine the long-term variables involved in the eSight device use.

11. Ethical and Regulatory Requirements

The following must be observed to comply with Health Canada and U.S. Food and Drug Administration regulations for conduct and monitoring of clinical investigations. These requirements also represent sound research practices.

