4.1. Schedule of Events

This section indicates data that will be collected for each subject. Subjects will be screened for enrollment prior to their initial visit. At the initial visit, subjects will provide informed consent and the investigator will obtain medical and ophthalmic history information as described in the CRF, and conduct a complete low vision assessment.

At various points through the protocol, decision points are identified as red boxes below.

STEP 1: Pre-Screen, Subject Profile, and Informed Consent

The Eyecare Physician at the Study Site will select potential candidates from the Site's regular flow of patients. In some cases, eSight may direct interested persons to the Site, who have contacted eSight directly.

Steps 1.01 through 1.03 may be administered by a Research Assistant or a similarly suitable staff person at the clinic (e.g.: CLVT, OT, etc.).

Step 1.01 Subject ID: When a potential Study Subject has been identified, the Site Administrator will assign a unique subject identification number from the site-specific list of numbers provided by eSight.

Step 1.02 Demographic Data: The Site Administrator will contact prospective study participants and obtain demographic data.

Step 1.03 Inclusion/Exclusion, and Informed Consent: The Site Administrator will work through the inclusion/exclusion criteria to verify the subject is qualified for the study, and then work with the subject through the informed consent process, obtaining their written approval to proceed. An IRB approved informed consent form will be used.

The site administrator will then provide to the Third Party Surveyor, contact information for the study subject in order to proceed with Step 2 below. The Third Party Surveyor will complete Step 2 and send that information back to the Site Manager for inclusion in the Subject's CRF.

STEP 2: Pre-Study LV Inventory Assessment & VA LV VFQ-48

Steps 2.01 through 2.03 will be administered by telephone using a Third Party Surveyor¹⁷.

Step 2.01 AT Inventory: The Third Party Surveyor will conduct a telephone interview with each subject. The purpose of this phone interview is to inventory the subject's current assistive devices and usage habits. This background information will be used by the study examiner to determine which visual aids will be used during benchmarking activities.

Step 2.02 Baseline VA LV VFQ-48 Questionnaire: Third Party Surveyor will work with the subject to complete the VA LV VFQ-48¹⁸ questionnaire.

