For example: if the subject reads all of the letters correctly on the 20/32 row and then 3 letters correctly on the 20/25 row, the Log Score would be calculated as follows:

$$\begin{aligned} \text{ETDRS Acuity Log Score} &= 20/32 \text{ Row} = 0.20, \text{ plus } 3 \text{ letters on } 20/25 \text{ row} \\ &= 0.20 - (3 \times 0.02) \\ &= 0.14 \end{aligned}$$

Snellen: Using the Subject's habitual corrective lenses (if applicable). For each eye independently, and then binocularly, determine the Snellen acuity²⁸.

Step 3.07 Mars Contrast Sensitivity Test: Test Contrast Sensitivity using the Mars chart. Mars test score sheet to be provided²⁹.

²⁶ On the CRF this will be a date range, because subjects will not recall with accuracy. E.g.: <6mos, 6-12mos, 1-2yrs, 2-5yrs, 5-10yrs, >10yrs.

²⁷ <https://www.good-lite.com/Details.cfm?ProdID=639>

²⁸ In some cases (e.g. dense scotoma) the test Subject may have difficulty reading ALL 5 letters on any line of the ETDRS chart, which limits the precise ETDRS scoring algorithm above. Adding Snellen allows greater flexibility in participant inclusion and data analysis.

²⁹ © 2003-2004 The Mars Perceptrix Corporation. <https://www.good-lite.com/Details.cfm?ProdID=549&category=26&Secondary=71>

Step 3.08 eSight Demonstration: eSight Eyewear will be demonstrated using a clinician's version of the device³⁰. The subject will be provided basic instruction on its use (zoom in/out, contrast adjust). The researcher will observe the Subject's performance in tests of, acuity (ETDRS) contrast performance, facial recognition, and reading (MNRead). These above tests are observational only, and are not recorded to provide a baseline performance measure with the eSight Device.

Step 3.09 Advancement Decision: At this point in the protocol the Subject and the Eyecare Physician will come to an agreement about whether to continue with the extended portion of the protocol evaluating eSight Eyewear. The decision will be based on a minimum 4-line ETDRS improvement using the device, the subject's performance of the various tasks above, their impressions of the eSight Eyewear demonstration, and the continued compliance with inclusion/exclusion criteria as defined in Sections 3.2 and 3.3 respectively. There is a subjective and personal aspect to this decision, not unlike a patient's decision about whether or not to purchase the device.

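### The Schedule of Events contains no adverse-event enquiry, and 52 to 68 days of home use pass without a scheduled contact, so mild and moderate events are likely to be under-recorded

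*Combined protocol and SAP*

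**What the plan says.** Section 4.1 opens by stating its scope: "This section indicates data that will be collected for each subject". It then sets out Steps 1.01 to 9.09. Section 7 sets the safety promise: "The incidence, severity and duration of all adverse events will be recorded according to the following scale". It grades severity and relatedness and requires severe AEs to reach the sponsor within 24 hours of awareness. It does not say who asks subjects about AEs, when, or with what question.

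The timing after the device is issued at Step 4 is:

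- Step 5: telephone calls labelled Day 9, 16 and 23, each with the sentence "This interaction can occur within a window of ± 2 days of Step 4".
- Step 6: "Step 6 must occur within 26-34 days of Step 4".
- Step 7: "The subject will again take the eSight Eyewear home with them, this time for a period of two more months". No call or visit is listed.
- Step 8: "Within 86-94 days of Step 4 (total of three months), subjects will be contacted by the Third Party Surveyor".
- Step 9: "Within 86-94 days of Step 4, subjects will be required to come to the clinic for a two hour assessment".

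Section 7 rates the overall AE risk as very low. It names injury through disorientation or poor hand-eye performance as the main hazard, with falls, trips and burns among its examples. Section 10 plans no AE summary.

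**The concern.** Section 7 makes a promise that the schedule gives nobody a stated occasion to keep. The hazards it names would arise mostly at home, where staff cannot see them. Without a scheduled question, a minor fall or a spell of disorientation reaches the record only if the subject raises it, staff happen to learn of it, or a CRF page that we cannot see prompts for it.

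The protocol's own rules give a reason to expect silence. Step 5 does not permit walking in immersive mode, and Section 5 lets a subject be removed for not complying. A subject who tripped while walking in that mode would have to volunteer a breach that could end participation.

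At stake is the reading of the safety result. A low AE count could reflect a safe device or the absence of a question, and the study could not tell these apart for non-severe events. Duration is also at risk, because an event early in Step 7 may first be mentioned about two months later.

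**Working it through.** **1. Is there an AE question at any step?** Content of each contact, from Section 4.1:

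- Steps 1 and 2: demographics, eligibility, consent, aid inventory, two questionnaires.
- Step 3: goals, cognition, SF-36, history, vision tests, demonstration (3.08), decision (3.09), baseline tests.
- Step 4: fitting, control training, tests with the device, first eSkills session.
- Step 5 calls: check the eSkills session and agree to the next; the third also confirms the next appointment.
- Step 6: progress, goals, further training, last eSkills session.
- Step 7: none.
- Step 8: questionnaires by telephone.
- Step 9: goals, SF-36, tests, open comments, device return.

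No AE enquiry appears. The closest item is the open comment at Step 9.09, which is not tied to AEs.

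**2. How long is the interval without scheduled contact?** Inputs, in days after Step 4: Step 6 = 26 to 34; Steps 8 and 9 = 86 to 94.

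- Plan's own figure first: window midpoints are 30 and 90, and 90 - 30 = 60 days. This matches the stated two months.
- Shortest: 86 - 34 = 52 days.
- Longest: 94 - 26 = 68 days.

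**3. What share of home use is that?** Share = gap / day of the final contact.

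- Lowest: 52 / 86 = 60%.
- Midpoint: 60 / 90 = 67%.
- Highest: 68 / 94 = 72%.

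For the 60 extended-arm subjects this is 60 x 52 = 3,120 to 60 x 68 = 4,080 subject-days. For comparison, if the month-one calls fall within 2 days of their labelled days, the longest month-one interval is 34 - 21 = 13 days.

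**4. What would incomplete capture do?** The documents give no AE rate and no capture rate, so this is an illustration with assumed values. With 0 events recorded in 60 subjects, the exact one-sided 95% upper limit on the recorded rate is 1 - 0.05^(1/60) = 4.9%. If a fraction s of affected subjects is captured, the limit on the true rate is 4.87% / s:

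- s = 1: 4.9%
- s = 0.5: 9.7%
- s = 0.25: 19.5%

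**5. Call windows.** Read literally, a window of 2 days either side of Step 4 runs from Day -2 to Day +2. The nearest labelled call is Day 9, which is 9 - 2 = 7 days outside it. Label and window cannot both hold. This is a separate drafting contradiction and no part of the AE argument.

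**The case against.** The strongest reply is that recording is already required. Section 7 covers all AEs, and the instrument for recording is the CRF, which Section 4 describes as divided into sections with staff assigned to each. Section 6 includes training in data collection and CRF administration. Neither the CRF nor the flowchart is available to us, so an AE page or prompt cannot be excluded. Staff can also see events directly at supervised visits, and sponsor staff attend Step 4. This stands as a limit on the claim. It does not remove it: a page for recording events is not a scheduled question, and Section 4.1 is where the schedule is set.

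Serious consequences also have routes of their own. Severe AEs are reported within 24 hours of awareness (Section 7), AEs that end participation are shared across sites (Section 8), and each withdrawal goes to the IRB within three days (Section 11.1). This stands too, and it confines the concern mainly to mild and moderate events that do not end participation.

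A reader might infer more than the documents support:

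- *That AEs are recorded only if volunteered.* The unseen CRF and direct observation by staff rule out so flat a statement. Likewise, Step 7 lacks scheduled contact; subjects may still call the site.
- *That 150-200 people try the device with no record of poor tolerance.* Section 3.1 gives 150-200 as anticipated screening enrolment. Some may stop at Step 2.04 or 3.02, before the demonstration, so the number exposed is not stated. For those who do not proceed after Step 3.09, the reason is noted on the CRF.
- *That Step 3.08 excludes AE recording.* Its sentence "These above tests are observational only, and are not recorded to provide a baseline performance measure with the eSight Device" concerns acuity, contrast, face and reading performance, not AEs.
- *That the AE rate will be too low by a known factor.* Under-recording is an inference, and the capture fractions above are assumed.

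**Conclusion.** The point holds as a gap in scheduled enquiry, not in the duty to record. No step in Section 4.1 describes an AE question, and the period without scheduled contact is 52 to 68 days, 60% to 72% of home use. Both findings come directly from the text. That mild and moderate events are likely to be under-recorded, and their duration poorly dated, is a judgement. It rests on the CRF not containing a prompt tied to each contact, and on subjects not reliably reporting minor events unasked. The size of any shortfall cannot be derived from the documents. The efficacy analysis is not affected. This is a cheap improvement worth making, and it would let a low AE count be read as evidence.

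**What to change.** Add one short fixed AE question set: fall, trip or collision; burn; disorientation or nausea; eye strain or headache; with dates of onset and end. Ask it at contacts that already exist: the end of Step 3.08 for everyone given the demonstration, Step 4, the three month-one calls, Step 6, Step 8 (with answers passed to the site) and Step 9. State in Section 10 that AE incidence will be reported separately for demonstrated subjects and for the extended arm. If the CRF already has an AE page, cite it in Section 4.1 at each of these steps.

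The cost is about one to two minutes per contact, a CRF page and amendment wording. The reported AE rate will probably rise, which should be expected and explained.

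Two additions are optional. A brief call midway through Step 7 would shorten the interval, at 60 extra calls and one more contact in a study with self-reported outcomes. Logged on-time hours could serve as exposure, but Section 10 says only that the logs may be used to check reported usage.

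Separately, reconcile the Day 9, 16 and 23 labels with the window attached to them.

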3.1. Sample Size

Subjects will undergo an initial screen and device demonstration (screening arm) to determine their suitability for an extended trial of the device (extended arm). The target number of subjects for the extended arm is 60 subjects.

Power analysis indicates that in a single tailed test with an alpha level of .05 and a power of .95, the relationship between anticipated effect size and the required sample size is shown in the chart at left. As indicated if we assume an effect size in the range 0.40 – 0.45¹², an appropriate n=60 (ten Study subjects per site).

¹¹ The term “functional visual performance” describes the wearer’s ability to perform various Activities of Daily Living (ADL) with better efficacy and speed than using habitual assistive technology devices. In some cases, because of the hands-free, variable distance, and portable attributes of eSight Eyewear, it is hypothesized that certain ADLs may be possible which were previously impossible or very difficult for certain subjects.

¹² This higher than typical anticipated effect size is an appropriate assumption for this Study design, because of prescriptive inclusion criterion (i.e.: not random population).

About $\frac{1}{3}$ to $\frac{1}{2}$ of subjects who fall into the acuity and visual field inclusion criterion described in Section 3.2 below, demonstrate acute objective improvement and an immediate aptitude with the device. Therefore, we anticipate a total of 150-200 to be enrolled in screening arm of the study, from which 60 will be selected to participate in the extended arm, a three month take-home trial of the device. We expect attrition to be low due to the rigorous screening process for participation.¹³

In addition to a clinician's unit, which incorporates trial lens frames and other unique features for fitting and demonstration, each Site will receive devices for Subjects as they are required. The Site and eSight can, at any time, agree to deploy additional devices to accelerate the collection of data.

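### Section 10 names only a start-to-end acuity comparison and gives no role to the same-visit without-device acuity that Step 9.03 already collects

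*Combined protocol and SAP*

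**What the plan says.** Section 10 (Analysis) fixes what will at least be reported: "The minimum objective data that will be reported is acuity, contrast, reading speed, without eSight Eyewear at the beginning of the trial". The other side of the comparison is the same measures taken with the device when the trial ends. Its methods paragraph adds repeated measures ANOVA, t-tests and non-parametric alternatives for all dependent variables, without saying which readings or visits enter. No primary endpoint is named.

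Section 4.1 schedules the readings:

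- **Step 3.06:** acuity without the device, by ETDRS or Snellen.
- **Step 3.09:** advancement to the extended arm. "The decision will be based on a minimum 4-line ETDRS improvement using the device", together with task performance, the subject's impressions and continued eligibility.
- **Step 4:** 25 to 30 days after the first visit. A footnote explains this window as keeping the Step 3 benchmarks valid.
- **Step 9.03:** 86 to 94 days after Step 4, acuity "with and without eSight Eyewear (ETDRS or Snellen").
- **Steps 9.04 and 9.06:** contrast and reading, with the device only.

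Section 10 does not mention the without-device reading from Step 9.03.

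**The concern.** This is a single-group study, so the acuity result depends entirely on which readings are subtracted. The named comparison takes its without-device side from one visit and its with-device side from another, about four months later. Two things other than the device can enter. One is any change in the eye over that interval, in conditions that include diabetic retinopathy, Stargardt's disease and macular degeneration. The other is chance error in the first reading, because subjects advance partly on a measured gain at that same visit: a first unaided reading that was poor by chance makes the 4-line rule easier to pass.

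The protocol itself treats the Step 3 benchmarks as time-limited, yet Section 10 relies on them well beyond that window. A same-visit pair free of both problems is already scheduled. If its use stays open, the choice between the two comparisons can be made after the results are known.

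**Working it through.** **The plan's own figure.** Section 3.1 assumes a "single tailed test with an alpha level of .05 and a power of .95" and an effect size of 0.40 to 0.45, giving "an appropriate n=60 (ten Study subjects per site"). A one-sided paired t-test with exact noncentral t needs 70 subjects at 0.40, 60 at 0.43 and 55 at 0.45. So 60 reproduces inside the stated range. The normal approximation at 0.425 agrees: ((1.645 + 1.645)/0.425)² = 59.9. The point below does not alter this. The documents give no acuity SD or within-subject correlation from which a different n could be derived.

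**Interval.** The shortest is 25 + 86 = 111 days and the longest 30 + 94 = 124 days. Against the 30-day upper limit meant to keep the Step 3 benchmarks valid, that is 111/30 = 3.7 to 124/30 = 4.1 times as long. For the Step 9.03 pair it is 0 days.

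**What each comparison estimates.** Work in logMAR (higher is worse). Let g be the device gain at the final visit, δ the change in unaided acuity since Step 3, e₁ the error in the first unaided reading, e₃ that in the final unaided reading and e₄ that in the final with-device reading.

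- Start-to-end gain: g − δ + e₁ − e₄
- Same-visit gain: g + e₃ − e₄
- Unaided change, Step 3.06 to Step 9.03: δ + e₃ − e₁

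The first equals the second minus the third, so reporting all three shows exactly how the named comparison is made up. The unaided change combines drift with the reversal of e₁ and does not separate them.

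**Regression to the mean in e₁.** Suppose Step 3.06 is the comparator for the 4-line rule and advancement is by truncation on the measured gain. With error SD e per reading, true-gain SD τ and selection intensity i, the mean of e₁ among those advanced is i·e²/√(τ² + 2e²). Section 3.1 gives one third to one half as the share showing immediate benefit (i = 1.09 to 0.80). The SDs are assumed. At 0.02 log units per letter (Step 3.06) and τ = 0.25:

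| e | √(τ² + 2e²) | half advance | one third advance |
|---|---|---|---|
| 0.08 | 0.274 | 0.019 (0.9 letter) | 0.025 (1.3 letters) |
| 0.10 | 0.287 | 0.028 (1.4 letters) | 0.038 (1.9 letters) |

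Wider assumptions are e = 0.03 to 0.10, τ = 0.15 to 0.35, and 30% to 40% advancing (60/200 to 60/150, since "we anticipate a total of 150-200 to be enrolled in screening arm of the study"). The term is then 0.003 to 0.056 logMAR, or 0.1 to 2.8 letters.

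**What stays.** The selected subjects' true gain exceeds that of the whole screened group by i·τ²/√(τ² + 2e²). Over the same wider range this is about 0.11 to 0.40 logMAR (5 to 20 letters), and it is in both comparisons. Example with τ = 0.25, e = 0.10 and 30% advancing (i = 1.16), checked by simulation: the excess gain over the screened group is 0.292 from start to end and 0.252 at the same visit. The switch removes 0.292 − 0.252 = 0.040, which is 0.040/0.292 = 14%. The other 86% remains.

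**The case against.** Section 10 states a minimum, names no primary endpoint and leaves the ANOVA readings open. The same-visit comparison is therefore unspecified, not ruled out. Step 9 is framed as assessing improvement against baseline and change over time, so the start-to-end comparison answers a question the protocol asks. All of this stands, and it is why that comparison should be kept alongside the new one.

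That Step 3.06 is the comparator for the 4-line rule is an inference. Step 3.09 does not name the without-device reading, and Step 3.06 allows Snellen while the rule is in ETDRS lines. Advancement also rests on judgement and preference, so pure truncation tends to overstate the regression term. This stands too. The term is conditional and small, and its SDs are assumed.

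A reader might infer that the Step 9.03 pair avoids selection. It does not: everyone at Step 9 has passed Step 3.09, and either comparison describes selected responders. A reader might also infer that drift is large relative to the 4-line rule. The documents give no drift figure. Section 3.3 excludes unstable vision and surgery or injections in the previous six months, which limits drift without ruling it out. Worsening would tend to understate the start-to-end gain, while regression to the mean would overstate it, so the net bias has no established sign.

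Finally, the order of testing at Step 9.03 is not stated, so practice or fatigue could affect the same-visit pair.

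None of this gives the Step 9.03 without-device reading a role in the analysis.

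**Conclusion.** The point holds in a limited form. The only acuity comparison that Section 10 names spans 111 to 124 days and so confounds the device effect with change in unaided acuity. If Step 3.06 fed the 4-line rule, it also carries an upward error of about 1 to 2 letters (e = 0.08 to 0.10, τ = 0.25, one third to one half advancing), or 0.1 to 2.8 letters under the wider assumptions. The size and direction of drift cannot be derived from the documents.

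The same-visit pair is the better estimate of the device-on effect at about three months, and its readings are already scheduled. It does not estimate the effect in the 150 to 200 people screened, and it offers nothing for contrast or reading speed, which have no without-device measurement at Step 9. The bias is modest; the case for acting is that the correction costs almost nothing and settles the choice of comparison in advance.

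**What to change.** In Section 10:

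1. Pre-specify the paired with-minus-without acuity difference at Step 9.03 as the estimate of the device-on effect.
2. Report it alongside the start-to-end comparison.
3. Report the without-device change from Step 3.06 to Step 9.03, using subjects tested on the same chart type at both visits.
4. State that the same-visit difference removes time drift and regression to the mean in the first reading, but not the selection of responders at Step 3.09, and that it applies to acuity only.

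The cost is a few lines of analysis text. No visit, test or subject is added, and the stated sample size is unaffected.
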